18.2 Coordinating Center

The DCRI will function as the CC for this trial as specified by the National Institute of Health and NHLBI HFN grant.

18.3 Biomarker Core Laboratory

The University of Vermont will serve as the core laboratory for measurement of HFN biomarkers. Plasma specimens will be collected at Study Visits 2, 3, 4, 5, 7, and 10 (0, 2, 4, 8, 12, and 24 weeks from randomization), processed at the clinical centers according to the procedures provided by the core laboratory, and shipped to the core laboratory on dry ice (Refer to Biomarker Core Laboratory Manual of Procedures). Any subjects who agree to participate in the HFN biorepository sub-study will have samples collected at the clinical sites and stored at the University of Vermont biomarker core laboratory.

19 REGULATORY ISSUES

19.1 Ethics and Good Clinical Practice

This study must be carried out in compliance with the protocol. These procedures are designed to ensure adherence to Good Clinical Practice, as described in the following documents:

1. ICH Harmonized Tripartite Guidelines for Good Clinical Practice 1996.
2. US 21 Code of Federal Regulations dealing with clinical studies (including parts 50 and 56 concerning informed consent and IRB regulations).

The investigator agrees to adhere to the instructions and procedures described in the protocol and thereby to adhere to the principles of Good Clinical Practice that it conforms to.

19.2 Institutional Review Board/Independent Ethics Committee

Before implementing this study, the protocol, the proposed informed consent form and other information to subjects must be reviewed by a properly constituted Institutional Review Board/Independent Ethics Committee (IRB/IEC). Documentation that the protocol and informed consent have been approved by the IRB/IEC must be given to the Coordinating Center before study initiation. Any amendments to the protocol, other than administrative ones, must be approved by this committee.

19.3 Informed Consent

The investigator or designee must explain to each subject (or legally authorized representative) the nature of the study, its purpose, the procedures involved, the expected duration, the potential risks and benefits involved and any discomfort it may entail. Each subject must be informed that participation in the study is voluntary and that he/she may withdraw from the study at any time and that withdrawal of consent will not affect his/her subsequent medical treatment

or relationship with the treating physician.

The informed consent form(s) must be submitted by the investigator for IRB/IEC approval. The Coordinating Center will supply template informed consent forms, which comply with regulatory requirements, and are appropriate for the study. Any changes to the template consent form suggested by the Investigator must be agreed to by the Coordinating Center before submission to the IRB/IEC, and a copy of the approved version must be provided to the Coordinating Center after IRB/IEC approval.

20 MONITORING

A CC monitor may visit sites during the study to verify that data collection is being handled properly. In addition, monitors may provide in-service training, review source, and address questions from site investigators and coordinators as needed. Remote monitoring activities will also be conducted to monitor compliance with the study protocol.

21 APPENDICES

21.1 Appendix A - Schedule of Assessments

Visit number	0	1	2	3	4	5	6	7	8	9	10	11	
Time of Visit	Enrollment	Run-in*	1 st dose	Dose titration (2 weeks)	Dose titration (4 weeks)	8 weeks	10 weeks	12 weeks	16 weeks	20 weeks	24 weeks	26 weeks	Unscheduled Visit for dose adjustment
Inclusion/Exclusion criteria	x		x										
Information & Informed consent	x												
Physical examination	x	x	x	x	x			x			x		x
KCCQ questionnaire	x				x			x			x		
Dispense study medication		x ¹	x	x	x	x		x			x		x
Laboratory test (routine)+	X [^]	x	x	x	x	x		x			x		x
Laboratory test (core)			x ²	x ³	x ²	x ²		x ²			x ²		
Adverse events		x	x ⁴	x	x	x	x	x	x	x	x		x
Telephone follow-up							x		x	x			
Telephone Safety Assessment												x	

* The Screening visit and Visit 1 may be combined at the investigator's discretion for subjects who are stable and for whom lab results have been reviewed as long as the investigator ensures the 1st dose of LCZ696 \geq 36 hours after last ACEI dose (if applicable). If not combined, Visit 1 should take place within 7 days of the Screening Visit

+ Local lab tests include the following: Sodium, Potassium, Chloride, CO₂/Bicarbonate, Total Calcium, Magnesium, BUN, Creatinine

[^] For Screening/Study Visit 0 only - Standard of care labs are acceptable, using results within 24 hours prior for hospitalized patients and within 7 days prior for outpatients.

¹ Open-label LCZ696 (50 mg po BID) during run-in phase

² BNP, core and Cystatin C

³ BNP and NT-proBNP only

⁴ Run-in failure patients should be contacted approximately 2 weeks after their last dose of study drug.

21.2 Appendix B - New York Heart Association Functional Classification

Class	NYHA Classification ¹⁰
I	Patients with cardiac disease but without resulting limitations of physical activity. Ordinary physical activity does not cause undue fatigue, palpitations, dyspnea, or anginal pain.
II	Patients with cardiac disease resulting in slight limitations of physical activity. They are comfortable at rest. Ordinary physical activity results in fatigue, palpitations, dyspnea, or anginal pain.
III	Patients with cardiac disease resulting in marked limitation of physical activity. They are comfortable at rest. Less than ordinary physical activity causes fatigue, palpitation, dyspnea, or anginal pain.
IV	Patients with cardiac disease resulting in inability to carry on any physical activity without discomfort. Symptoms of cardiac insufficiency or of the anginal syndrome may be present even at rest. If any physical activity is undertaken, discomfort is increased.

---

## 1. Overview

### 1.1 Synopsis

The *Entresto™ (LCZ696) In Advanced Heart Failure (LIFE)* study is a randomized, double-dummy, active-comparator trial to assess the effect of LCZ696 (sacubitril and valsartan) versus Valsartan, with dose up-titration, on the proportional change from baseline in the AUC for NT Pro BNP levels. The eligible patient population consists of those with symptomatic, advanced heart failure due to left ventricular systolic dysfunction. Randomized study treatment will take place for a total of 24 weeks.

### 1.2 Study Treatments

Each patient will be randomized to receive either LCZ696 (sacubitril and valsartan) + valsartan-placebo or Valsartan + LCZ696-placebo. Study treatment will be titrated to the target dose of 200 mg LCZ696 as two 100 mg LCZ696 and 2 placebo tablets po BID or to the target dose of 160 mg Valsartan as two 80 mg Valsartan and 2 placebo tablets po BID. Randomized subjects will receive the first dose of study drug as follows:

- For subjects not previously taking an ACE Inhibitor (ACEI) or Angiotensin Receptor Blocker (ARB), previously taking an ACEI or ARB at a low dose, or subjects who have an eGFR < 30 mL/min/1.73m^2, the starting dose of valsartan will be 40 mg po BID and the starting dose of LCZ696 will be 50 mg po BID.
- For subjects taking an ACEI or ARB at greater than low dose, the starting dose of valsartan will be 80 mg po BID and the starting dose of LCZ696 will be 100 mg po BID.

Dose adjustments will be performed every 2 weeks by doubling the dose of LCZ696 or valsartan up to the target maximum dose. The doses of LCZ696 are 50 mg (one 50 mg active and one placebo tablet), 100 mg (one 100 mg active and one placebo tablet) and 200 mg (two 100 mg active and two placebo tablets). The doses of valsartan are 40 mg (one 40 mg active and one placebo tablet), 80 mg (one 80 mg active and one placebo tablet), and 160 mg (two 80 mg active and two placebo tablets).

## 2. Study Design

### 2.1 Overview

The LIFE study is a randomized, double-dummy, active-comparator study in heart failure patients with reduced ejection fraction. A planned total of approximately 400 patients will be randomized in the study.

The randomized treatments in this study are blinded. Treatment is expected to last for 24 weeks.

The over-arching hypothesis is that, compared to Valsartan alone, treatment with LCZ696 will lead to improvements in NT Pro BNP levels, which reflect hemodynamic and clinical status.

### 2.2 Randomization

Patients are randomized in a 1:1 ratio to either LCZ696 + Valsartan-placebo or Valsartan + LCZ696-placebo. The randomization scheme consists of a permuted block design with stratification by clinical site and atrial fibrillation status.

### 2.3 Data Sources

A database of case report form and biomarker core lab data will be created in Inform, and the data then transferred to SAS for analysis. The randomized treatment assignment will be provided through data provided by the Webez system, an Almac Clinical Services web-based randomization system. The data is stored on Solaris server uxctstp01 in the folder /dcric/ct/hf\_net/LIFE/data.

### 3. Analysis Population and Missing Data

All randomized patients will be included in the analysis population for assessing the primary, secondary, tertiary, and exploratory endpoints. All endpoints will be analyzed on an intent-to-treat basis.\*

However, as described in subsequent sections of this document, some patients may be excluded from certain analyses if key data elements are missing. With the extensive efforts being made in collaboration with the clinical sites to ensure data quality and completeness, it is expected that exclusion of patients for any endpoint analysis will be minimal. The specific endpoint descriptions in Sections 9 through 12 describe the circumstances that would lead to a patient being excluded from a specific analysis.

#### \* Analysis Modifications to Address COVID-19 Pandemic

The coronavirus COVID-19 pandemic has had a major impact on the performance of the LIFE trial. It was anticipated that patients will have greater difficulty attending study visits on their planned schedule due to restrictions on outpatient visits at many institutions. Therefore, patients will be unable to participate in study-related procedures such as biomarker sample collection, which comprises the primary endpoint for this trial. Additionally, due to restrictions on clinic access and potential concerns with patients going to the emergency department where exposure risk to COVID-19 is increased, we expect reporting of clinical endpoints such as emergency department visits and even hospital admissions to be impacted by the pandemic.

Therefore, due to the unexpected disruption brought on by the COVID-19 pandemic, the analysis plan was amended to restrict the reported program analyses to those patients that had their Week 12 visit prior to March 1, 2020, when the COVID-19 pandemic became more active in the continental United States. This translated to restricting the reported analyses to patients that were randomized on December 7, 2019 or earlier. Additionally, any study data collected after March 1, 2020 were excluded from the analyses for those patients randomized on or prior to December 7, 2019. This amended population will be labeled as the pre-COVID-19 population within the analysis plan.

The original protocol-specified analyses were to be conducted on all randomized patients using all available information. Those analyses will still be performed but will be considered to be sensitivity analyses.

Of the 365 patients randomized, 335 will be included in the pre-COVID-19 population. Twenty five of the 335 patients will have some visit information removed due to study visits occurring March 1, 2020 or later. The

remaining 30 patients will only contribute to the original protocol-specified analyses, now part of the sensitivity analyses.

#### 4. General Methodology

Medians, 25th and 75th percentiles will be presented for continuous variables; the number and percentage of patients in each category will be presented for categorical variables. For all endpoints a p-value  $\leq 0.05$  will be considered statistically significant and all tests will be 2-sided. Analyses will be performed using validated SAS software (SAS Institute, Inc., Cary, NC). Appropriate statistical models will be used to examine the effect of treatment on both the primary, secondary, and tertiary outcomes in the study.

The modeling that will be used for each endpoint will be detailed within each endpoint description section.

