16 STATISTICAL METHODS AND DATA ANALYSIS

16.1 General Design Issues

All planned analyses will be prospectively defined for this study and approved by the CC prior to unblinding of data. The statistical analysis plan (SAP) will contain detailed information regarding the data analysis. The SAP will be finalized prior to trial completion and will be approved by the coordinating center statistical team as well as the National Heart, Lung, and Blood Institute (NHLBI) program officer.

Analysis of the LIFE Study will be based on intention to treat (ITT). That is, subjects will be analyzed (and endpoints attributed) according to the treatment strategy to which subjects are randomized, regardless of subsequent additional post-randomization treatment and medical care. The ITT population will correspond to all randomized subjects.

Statistical comparisons will be performed using two-sided significance tests. Baseline demographic and clinical variables will be summarized for each randomized arm of the study. Descriptive summaries of the distribution of continuous variables will be presented in terms of percentiles (e.g., median, 25th and 75th percentiles) along with means and standard deviations. Categorical variables will be summarized in terms of frequencies and percentages.

In addition, exploratory analyses will be performed to help explain and understand findings

observed from the planned analyses. Statistical tests with a 2-sided p-value <0.05 will be considered statistically significant, unless otherwise stated. Analyses will be performed using SAS software (SAS Institute, Inc, Cary, NC).

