16.5 Analysis of Secondary, Tertiary and Exploratory Endpoints

The key secondary endpoint, *days alive and out of hospital at 6 months, not listed for transplant (status 1A, 1B or 1-4) or undergoing transplant, implanted with an LVAD, maintained or started on continuous inotropic therapy for ≥ 7 days, or has had two hospital admissions for HF (other than the index admission*)*, will be analyzed using a regression model with indicator variables for the treatment assignment and atrial fibrillation at enrollment. For time-to-event endpoints, the

Cox regression model for survival data will be used to test the statistical significance of differences in mortality between the treatments. Kaplan-Meier curves will be generated to graphically display the mortality rates as a function of time from randomization in each treatment. Continuous endpoint data will be modelled using general linear models. Mixed models will be used for the analysis of longitudinal data. The unmatched win ratio approach of Pocock et al. will be used to analyze the modified composite endpoints.¹¹

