##### Secondary Endpoints (Tolerability)

#2: Tolerability measured as number of subjects achieving a target dose of 25%, 50% or 100% of valsartan or LCZ696.

#3: Tolerability measured as number of subjects developing hypotension (SBP  $\leq 85$  mmHg) with symptoms.

#4: Tolerability measured as number of subjects developing worsening renal function (eGFR  $< 20$  ml/min/1.73m^2).

#5: Tolerability measured as number of subjects developing moderate ( $> 5.5$  mmol/L) or severe ( $\geq 6$  mmol/L) hyperkalemia.

See Section 10 for a detailed description of each secondary endpoint, including rules used for handling incomplete data.

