#### 7. Tertiary Endpoints

##### Tertiary Endpoints

#1: Time to death through 24 weeks.

- #2:** Time to cardiovascular death through 24 weeks.
- #3:** Time to first heart failure hospitalization through 24 weeks.
- #4:** Time to death or first heart failure hospitalization through 24 weeks.
- #5:** Time to cardiovascular death or first heart failure hospitalization through 24 weeks.
- #6:** Total number of HF hospitalization admissions through 24 weeks.
- #7:** Number of subjects on continuous inotropic therapy  $\geq 7$  days after discharge from the index hospitalization through 24 weeks.
- #8:** Number of subjects listed for transplant (1A, 1B or 1-4), transplanted or implanted with an LVAD through 24 weeks.
- #9:** Change in eGFR levels compared to baseline. Renal function was assessed at baseline, weeks 2, 4, 8, 12, and 24.
- #10:** Change in cystatin C levels compared to baseline. Renal function was assessed at baseline, weeks 2, 4, 8, 12, and 24.
- #11:** Number of subjects with unanticipated use of IV diuretics (outpatient, ER or inpatient) through 24 weeks.
- #12:** Change in AUC in the Kansas City Cardiomyopathy Questionnaire (KCCQ) at 4, 12, and 24 weeks compared to baseline.
- #13:** The change in the AUC for the ratio of NT Pro BNP/BNP from baseline to weeks 2, 4, 8, 12, and 24.
- [Note: Tertiary Endpoint #13 will only be assessed on the first 200 patients randomized, as generated for the Interim Analysis. A decision was made by the Executive Committee to not assay for BNP at trial completion for the remaining randomized patients]

See Section 11 for a detailed description of each tertiary endpoint, including rules used for handling incomplete data.

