## 8. Exploratory Endpoints

### Exploratory Endpoint

**#1:** A four level modified clinical composite endpoint including 1) death, 2) LVAD or Heart Transplant (including listing status of 1A, 1B or 1-4), 3) multiple HF hospital admissions, and 4) single HF admission.

See Section 12 for a detailed description of each tertiary endpoint, including rules used for handling incomplete data.

[figure not shown]

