## 10.2 – Secondary Endpoint #2

Endpoint Description: Tolerability measured as number of subjects achieving a target dose of 25%, 50% or 100% of valsartan or LCZ696, using the pre-COVID-19 population.

Response Variable Definition: Due to limited documentation concerning reasons for dose reduction, four versions of this endpoint will be calculated:

- 1) maximum study drug dose started (including 0),
- 2) dose patient took for the most number of days (including 0),
- 3) last dose patient was taking (including 0), and
- 4) last dose patient was taking (excluding 0).

There are 4 ordered values possible based upon the coding of the responses. Each response will be coded to represent 0% of target (no drug), 25% of target (50 mg LCZ696/40 mg Valsartan), 50% of target (100 mg LCZ696/80 mg Valsartan) or 100% of target (200 mg LCZ696/160 mg Valsartan). The number of evaluable days will be based on time from randomization to earliest date of Week 24, Death, Consent Withdrawal, or Last Contact.

Additional Covariates in Addition to Randomized Treatment: atrial fibrillation status at time of randomization

Handling of Dropouts and Missing Data: No adjustment will be made for missing data.

Sensitivity Analysis: Re-calculate the endpoint analysis using the original ITT population.

Statistical Tests: An ordinal logistic regression model (PROC LOGISTIC in SAS) will be used to estimate and statistically compare whether there is differential study drug dose achievement between the treatments.

Interpretation of Treatment Comparison: More patients achieving/tolerating higher doses indicates better tolerance of LCZ696 versus Valsartan.

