## 11.12 – Tertiary Endpoint #12

Endpoint Description: Change in AUC in the Kansas City Cardiomyopathy Questionnaire (KCCQ) compared to baseline – both for overall and clinical summary scores, using the pre-COVID-19 population.

Response Variable Definition: The KCCQ questionnaire was completed at Screening (considered Baseline for this analysis), Week 4, Week 12 and Week 24. The endpoint will be derived in a similar fashion to the primary endpoint (see 9.1).

Additional Covariates in Addition to Randomized Treatment: atrial fibrillation status at time of randomization, appropriate baseline value of each KCCQ score

Handling of Dropouts and Missing Data: If missing KCCQ score at Week 24, use last observation carried forward (LOCF) from previous post-Baseline time point with available KCCQ score data. No adjustment will be made for missing Baseline results.

Sensitivity Analysis: Re-calculate the endpoint analysis using the original ITT population.

Statistical Tests: A general linear model (PROC GLM in SAS) will be used to test the significance of differences in the area under the curve for the each KCCQ score between the two treatment arms.

Interpretation of Results: A higher KCCQ score indicates an improved KCCQ score in the LCZ696 arm versus Valsartan.

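### SAP 4 lets any of 19 non-primary endpoints be called statistically significant at 0.05, with no testing order, adjustment or nominal label

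*SAP*

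**What the plan says.** SAP section 4 sets one decision rule for all endpoints: a p-value of 0.05 or less "will be considered statistically significant and all tests will be 2-sided". Protocol 16.1 has the same default: "Statistical tests with a 2-sided p-value <0.05 will be considered statistically significant, unless otherwise stated". Nothing different is stated later for any non-primary endpoint. The only other alpha is 0.001, in SAP section 14, for the interim look at the primary.

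The rule covers these endpoints beyond the primary:

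- Five secondary endpoints: one efficacy and four tolerability (SAP section 6).
- Thirteen tertiary endpoints (SAP section 7), the last being "The change in the AUC for the ratio of NT Pro BNP/BNP from baseline to weeks 2, 4, 8, 12, and 24".
- One exploratory endpoint (SAP section 8): "A four level modified clinical composite endpoint including" death, LVAD or transplant, and HF admissions.

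Two of these carry more than one test. For the dose endpoint, "four versions of this endpoint will be calculated" (SAP 10.2), and none is named as the main one. KCCQ is analysed "both for overall and clinical summary scores" (SAP 11.12).

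Protocol 16.5 singles out days alive and out of hospital with the words "The key secondary endpoint". It attaches no order or condition to that label.

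**The concern.** A rule that calls every result at 0.05 significant does not limit how many chances the trial has to make a claim. If the biomarker primary is neutral, nothing in the plan stops a report from presenting one favourable clinical or tolerability result as statistically significant, and the reader could not tell it from a chance finding among about 20 tests.

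The plan also uses 0.05 inferentially below the primary. Protocol 16.2 gives power at two-sided 0.05 for death or first HF re-admission, which corresponds to a tertiary endpoint. SAP section 14 reports that conditional power was calculated for the secondary endpoints as well as the primary. In addition, SAP tertiary #2 (cardiovascular death) and #5 (cardiovascular death or HF hospitalisation) are not in protocol 13.3, yet they fall under the same rule.

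**Working it through.** **The plan's own figure.** Neither document states a family-wise error rate, so there is none to reproduce. The nearest is the protocol 16.2 power for death or first HF re-admission at two-sided 0.05. A two-proportion calculation for 40% versus 25% gives 0.896 with 200 per arm and 0.880 with 190 (stated: 88%). For 40% versus 30% it gives 0.555 with 200 per arm (stated: 55%). The stated powers therefore reflect an unadjusted 0.05.

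**Count of tests.**

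- Endpoints: 5 + 13 + 1 = 19.
- With two KCCQ scores: 19 + 1 = 20.
- With all four dose versions as well: 20 + 3 = 23.
- Check on the 13: protocol 13.3 lists 10. The SAP splits eGFR from cystatin C (+1) and adds two cardiovascular-death endpoints (+2).
- Not counted: the mid-p test for each SAE preferred term (SAP 13.1), subgroups (SAP section 15), and repeats in the original ITT population.

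**Independent tests, all non-primary nulls true.**

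- Either direction, 1 − 0.95^k: 0.623 for k = 19; 1 − 0.358 = 0.642 for k = 20; 0.693 for k = 23.
- Favouring LCZ696 only, 1 − 0.975^k: 0.38 for k = 19; 1 − 0.603 = 0.40 for k = 20; 0.44 for k = 23.

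**Correlated tests.** The documents give no correlations, so these are assumed. With a common correlation ρ between test statistics, write each as √ρ·G + √(1 − ρ)·E. Here G is a shared standard normal variable and E is independent noise. The chance of at least one rejection is 1 minus the average over G of [P(no rejection given G)]^k. For k = 20:

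| ρ | Either direction | Favouring LCZ696 |
|---|---|---|
| 0 | 0.64 | 0.40 |
| 0.3 | 0.54 | 0.28 |
| 0.5 | 0.42 | 0.21 |

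The either-direction figure falls below one half at ρ of about 0.35 for 19 tests, 0.37 for 20 and 0.43 for 23.

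**A structure closer to this trial.** Eleven endpoints (secondary #1, tertiary #1 to #8 and #11, exploratory #1) draw largely on the same deaths, HF admissions, LVAD or transplant events and inotrope use. Three are renal (secondary #4, tertiary #9 and #10). The rest are treated as separate endpoints. With assumed between-block correlation of 0 to 0.2, 400,000 simulated draws give, in either direction:

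| Within-block correlation | 19 tests | 23 tests |
|---|---|---|
| 0.5 | 0.51–0.53 | 0.57–0.60 |
| 0.7 | 0.44–0.46 | 0.50–0.53 |
| 0.9 | 0.36–0.38 | 0.41–0.42 |

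**Primary endpoint.** An interim look at 0.001 followed by a final test at 0.05 gives a type I error of about 0.050. The number of other endpoints does not change it.

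**The case against.** The case for leaving the plan alone has four parts.

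- **Tiers.** There is one primary endpoint, and the labels secondary, tertiary and exploratory already signal supportive status. This stands as far as the main inference goes. It does not answer the point, because SAP section 4 applies the word significant to all tiers and no text ties one tier to another.
- **Tolerability.** Four of the five secondary endpoints are tolerability measures. Adjustment there would make a harm harder to declare, and protocol 11.6 itself reports more symptomatic hypotension with LCZ696 than with enalapril (18% versus 12%). This stands, and the fix leaves these comparisons unadjusted.
- **Interpretation lines.** A reader might infer that the interpretation line under each SAP endpoint turns a p-value into a benefit claim. The documents do not support that. The lines mainly say which direction is favourable and set no significance rule. The problem is the rule in section 4.
- **Gating.** Testing the key secondary only after the primary is one choice among several and costs power for the clinical claim. This also stands, so the gate is offered as an option only.

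**Conclusion.** The gap is real and can be confirmed from the text whatever correlation is assumed: the plan states a rule that permits uncontrolled significance claims from 19 endpoints. The size depends on unstated correlations and on all non-primary nulls being true. For 20 tests it runs from 0.64 (independent) to 0.42 (correlation 0.5) in either direction, and from 0.40 to 0.21 in favour of LCZ696. Because so many clinical endpoints share events, independence is the least plausible case. Even 0.21 is well above the 0.025 chance that a single two-sided test falsely favours LCZ696.

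Two stronger readings are tempting. One is that a false significant result is more likely than not. That needs weak correlation across the whole set, which the overlapping endpoints make doubtful; the block calculation above falls on both sides of one half. The other is that a false claim of benefit is more likely than not. No calculation here supports that: even 23 independent tests give 0.44. Nor is the trial's main result in doubt, since the primary keeps its error rate. The point concerns how results beyond the primary may be described.

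**What to change.** Replace the SAP section 4 sentence with text to this effect: significance at two-sided 0.05 applies to the primary endpoint only; all secondary, tertiary and exploratory results are given with 95% confidence intervals and nominal p-values and are not described as statistically significant; tolerability and safety comparisons are reported unadjusted, as signals. Align the default in protocol 16.1. Mark tertiary #2 and #5 as not listed in protocol 13.3.

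If the sponsor wants a formal claim on days alive and out of hospital, one option is to test it at 0.05 only after a significant primary. Because SAP section 14 shows that conditional power for secondary endpoints had already been calculated at the interim, the SAP should then state when the gate was adopted and whether those choosing it had seen those results.

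The cost is a few sentences. No planned analysis is dropped and the primary loses no power. The downside is that no non-primary endpoint can carry a formal significance claim. With the gate, the key secondary can carry one only when the primary succeeds, so its power for that claim is the joint probability that both tests succeed, and a real clinical effect could not be called significant if the biomarker is neutral.
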